2.2 Analysis sets

The analysis sets to be used are defined as below.

All efficacy analyses will be performed on subjects in FAS who have completed treatment. The Safety Set will be used for all the safety analysis.

Full Analysis Set (FAS)

The FAS include all enrolled subjects to whom the study treatment has been assigned regardless of whether or not they have received at least 1 dose of study treatment or have at least 1 post-baseline assessment.

Safety Set (SAF)

The SAF will consist of all subjects who received at least 1 dose of study treatment.

2.2.1 Subgroup of interest

- The primary analysis will be conducted on a subgroup of subjects with stuttering (duration of priapic events from 1 to <=4 hours) and acute priapism. Acute priapic events are defined as an unwanted, painful erection that lasts more than 4 hours and need a visit to emergency room.

- Additional subgroup analysis will be performed based on duration of priapic events (i.e., <1, 1 to ≤4, >4 to ≤6, >6 to ≤12, >12 hours).
- Subgroup analysis of the primary endpoint will also be performed based on the number of priapic events categories (i.e. <7, 7 – 13, 14 – 21, ≥ 22) at baseline (12 weeks) and baseline (adjusted for 26 weeks). The priapic events categories may be re-grouped to ensure that there is adequate number of subjects in each category for analysis.
- Note that, subgroup analyses of the primary endpoint by age group will only be performed if an adequate number of subjects are present in each subgroup class.

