c Certain adverse events reported in the AE/SAE eCRF as Infusion Related Reactions will require the IRR eCRF to be completed.

d Local sampling for platelet assessment will be performed throughout the trial for all subjects.

e The date, number, and duration of the priapic events in the 14-week period prior to consenting will be captured in a separate CRF.

f Subjects who will receive commercially approved crizanlizumab approximately 4 weeks after their last dose of study treatment, do not need to complete the 105-day follow-up.

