2.5.2 Statistical hypothesis, model, and method of analysis

It is expected that crizanlizumab treatment reduces priapic events by at least 25% in SCD subjects with priapism.

Demonstration of significant percent reduction from baseline in priapic events will be evaluated using following hypothesis:

$H_0: p < 0.25$, where p is the percent reduction in priapic events by 26 weeks.

$H_1: p \geq 0.25$, where p is the percent reduction in priapic events by 26 weeks.

If the above null hypothesis is rejected, significant reduction in priapic events will be demonstrated statistically.

Assuming uniformity in the occurrence of priapic events before exposure to crizanlizumab treatment, baseline will be adjusted for 26 weeks for analysis purpose.

Baseline (adjusted for 26 weeks): Number of priapic events in 12 weeks screening period * (26/12) and percentage change from baseline = (Post baseline value –Baseline (adjusted to 26 weeks) value) * 100 / Baseline (adjusted to 26 weeks) value.

Percentage reduction from baseline is the negative percentage change from baseline.

Percent reduction from baseline in priapic events will be tested using a non-parametric test (i.e., Wilcoxon's Sign Rank test) and p-value will be reported. The study would be declared a success, if percentage reduction in events is $\geq 25\%$ and $p < 0.05$ is obtained from Wilcoxon's Sign Rank test.

Hodges-Lehmann estimate of median percent reduction in priapic events will also be reported, along with corresponding 95% confidence intervals.

Number of priapic events will be summarized at baseline (adjusted for 26 weeks) and by Week 26, and percent reduction from adjusted baseline by Week 26 will be summarized by n, mean, standard deviation (SD), lower quartile (Q1), median, upper quartile (Q3), minimum and maximum.

Graphical representation of percentage reduction, through box plot or bar graph or waterfall plot, will be performed as appropriate by 26 weeks.

In addition, subgroup analysis of the primary endpoint will be performed based on the number of priapic events categories (i.e. <7, 7 - 13, 14 - 21, \geq 22) at baseline (12 weeks) and baseline (adjusted for 26 weeks). Additional analyses of the primary endpoint will also be performed for the subgroups of subjects with stuttering and acute priapism. Summary statistics for percentage reduction by 26 weeks will be presented for each subgroup.

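### Classing subjects by the screening count that is also the endpoint's denominator produces a rising gradient with no drug effect; on the 26-week-adjusted scale the cut points also omit a count of 10

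*SAP*

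**What the plan says.** SAP 2.2.1 states: "Subgroup analysis of the primary endpoint will also be performed based on the number of priapic events categories", with the classes "<7, 7 – 13, 14 – 21, ≥ 22) at baseline (12 weeks) and baseline (adjusted for 26 weeks". SAP 2.5.2 repeats the classes on both scales. Protocol 12.4.2 lists the same four classes at baseline without naming the scale.

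SAP 2.5.2 defines the adjusted baseline as "Number of priapic events in 12 weeks screening period * (26/12") and divides the change by that value: "100 / Baseline (adjusted to 26 weeks) value". The classing variable and the denominator are therefore one number.

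Reporting is descriptive: "Summary statistics for percentage reduction by 26 weeks will be presented for each subgroup". The only flexibility is that "The priapic events categories may be re-grouped to ensure that there is adequate number of subjects in each category for analysis". Neither document gives a rule for non-integer values at the class boundaries, and neither mentions regression to the mean. Protocol 4.3 confirms that there is no control group.

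**The concern.** A screening count is the subject's underlying rate plus chance. A chance-high count moves the subject into a higher class and enlarges his denominator, so the treatment-period count looks like a reduction. A chance-low count does the reverse. In a randomised trial the control arm would show the same pattern and expose it. Here nothing does.

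The table could therefore be read as showing that the drug works in frequent-event patients and fails, or harms, in infrequent ones. That pattern would be expected from an inactive drug.

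The second problem is clerical. Whole-number cut points suit counts, but the adjusted baseline moves in steps of 26/12 = 2.17, so a value can fall between two printed classes.

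**Working it through.** **The plan's own figure.** Protocol 12.9 and SAP 3 give 34 evaluable subjects for about 80% power, from a mean of 10.0, a 25% reduction (2.5 events), an SD of the difference of 5.0 and two-sided alpha 0.05. A one-sample t test at n = 34 has power 0.808, and a simulated signed-rank test 0.80. Dropout: 34/0.95 = 35.8, so 36 enrolled. The figure reproduces and does not depend on the subgroup classes.

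**Cut points, adjusted scale.** Entry requires at least 3 screening events, so the possible values are:

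- 3 × 26/12 = 6.5
- 4 to 6 events: 8.67, 10.83, 13.0
- 7 to 9 events: 15.17, 17.33, 19.5
- 10 events: 21.67
- 11 events: 23.83

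The value 21.67 is above 21 and below 22. It is the only eligible count that is lost. The <7 class can hold only subjects with exactly 3 events. On the 12-week scale, 10 sits in 7-13.

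**Mechanism, one subject.** Take a steady true rate of 10 per 12 weeks and no drug effect. The expected 26-week count is 21.67.

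- Screening count 6 (adjusted 13.0): 100 × (1 - 21.67/13.0) = -67%.
- Screening count 14 (adjusted 30.33): 100 × (1 - 21.67/30.33) = +29%.

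**Null simulation.** From the documents: 14-week pre-screening, 12-week screening and 26-week treatment periods; entry rules of at least 4 pre-screening events, at least 3 screening events and at least 1 in the last 4 weeks; mean 10.0. Assumed: Poisson counts with an unchanged rate for each subject, and a gamma between-subject distribution with shape k = 1, 2 or 4 (CV 1 to 0.5), because the documents give no between-subject variance. The period to which the 10.0 belongs is not clear, so both readings are shown; 10 per 26 weeks is 10 × 12/26 = 4.62 per 12 weeks. Median percent reduction by adjusted class:

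| Mean | k | <7 | 7 to <14 | 14 to <22 | ≥22 | Highest minus lowest |
|---|---|---|---|---|---|---|
| 10 per 26 wk | 4 | -38 | -2 | 21 | 31 | 69 |
| 10 per 26 wk | 2 | -38 | -2 | 14 | 22 | 60 |
| 10 per 26 wk | 1 | -23 | -4 | 8 | 15 | 38 |
| 10 per 12 wk | 4 | -69 | -29 | -3 | 12 | 81 |
| 10 per 12 wk | 2 | -54 | -20 | -2 | 8 | 62 |
| 10 per 12 wk | 1 | -38 | -15 | 1 | 6 | 44 |

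Treatment counts are whole numbers, so most medians move by a point or two between runs. The lowest class moves in larger steps: 8 events gives 100 × (1 - 8/6.5) = -23 and 9 events gives -38. In the third row the median sits on that step, and repeat runs give either value.

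On the 12-week scale the spread is about 23 to 49 points. At k = 1 the medians are -8/11/14/16 (mean 10 per 26 weeks) and -15/2/5/8 (10 per 12 weeks).

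**Wider range.** With CV from 0 to 1.5 and extra within-subject variation of 0 or about 0.05, the direction never changes. The smallest spread is 31 points on the adjusted scale and about 16 on the 12-week scale.

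**At the planned size.** In null trials of 34 subjects with the extra variation, the median reduction was higher for adjusted baseline ≥14 than for <14 in 77 to 99.8% of trials, and by 25 points or more in 47 to 99%.

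**Class sizes.** A count of 10 occurs in about 5 to 8% of eligible subjects (34 × 0.05 = 1.7; 34 × 0.08 = 2.7). The adjusted <7 class holds 8 to 12% at mean 10 per 26 weeks and 3 to 4% at 10 per 12 weeks.

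**The case against.** The strongest defence is that the table is descriptive. No subgroup test, interaction test or decision rule is attached to it, so the documents do not themselves plan the inference feared here. That stands, and it keeps the point minor. A table that leans one way under no effect still needs a caution.

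The extreme medians come from a very small class, perhaps 1 to 4 of 34 subjects, which the re-grouping sentence could merge with the next. That also stands in part. Merging all counts of 6 or fewer raises the lowest null median to about -8 (mean 10 per 26 weeks), or to between -31 and -15 (10 per 12 weeks). The spread to the top class is then 15 + 8 = 23 to 31 + 8 = 39 on the first reading, and 6 + 15 = 21 to 12 + 31 = 43 on the second. Re-grouping reduces the artefact without removing it. It also gives no home to 21.67, since its stated purpose is adequate numbers.

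Three stronger readings are tempting and not supported:

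- A reader might infer that 10 events is unclassified throughout. It is lost on the adjusted scale only.
- A reader might infer a large false benefit in frequent-event subjects whatever the inputs. If the mean is 10 per 12 weeks, the top adjusted class shows only 6 to 12%, and most of the spread lies at the low end.
- A reader might conclude that the 14-week pre-screening count should replace the screening count. It is recorded ("The date, number, and duration of the priapic events in the 14-week period prior to consenting will be captured in a separate CRF", Protocol Table 8-1), but the rationale in Protocol Amendment 2 reports difficult recall and uneven quality between patients and sites. The entry minimum also leaves an opposite gradient, about 15/8/1/-2 at k = 4 and mean 10 per 26 weeks, and that figure assumes no recall error.

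**Conclusion.** The concern holds as a presentation fault in a planned descriptive table. The direction of the false gradient was the same in every setting tried. Its size rests on the assumed between-subject spread and on which period the mean of 10 refers to: about 38 to 81 points on the adjusted scale and 23 to 49 on the 12-week scale for k between 1 and 4. For comparison, the target effect is a 25% reduction. The gap at 21.67 and the one-value <7 class are plain arithmetic and need no assumption, but they concern the adjusted scale only.

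Nothing here bears on the primary signed-rank test or the sample size, and a reader should not infer that it does. The change is worth making because it is cheap, not because a trial conclusion depends on it.

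**What to change.** In SAP 2.2.1 and 2.5.2:

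1. Write the adjusted-scale classes as contiguous intervals: <7, 7 to <14, 14 to <22, ≥22. A count of 10 then falls in 14 to <22.
2. Print beside each class, on both scales, the median percent reduction expected with no drug effect under the entry rules, with its assumptions and a range over the between-subject spread and the mean rate.
3. State under the table that the classing count is also the denominator, and that differences between classes are not evidence of a differential drug effect.
4. Optionally add a companion table by the 14-week pre-screening count, noting its recall quality and its smaller, opposite gradient. It should not replace the planned table.

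The cost is SAP wording and one short simulation; no new data are needed. The downside is that the no-effect reference depends on a between-subject variance that the documents do not give, so it should be shown as a range.

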2.3 Subject disposition, demographics and other baseline characteristics

2.3.1 Subject disposition

The following summaries will be provided for subject disposition in different study phases:

- Number (%) of subjects who were screened, screen failures, reasons of discontinuation from screening phase (based Screening phase disposition page), with % based on all subjects in Screening phase).
- Number (%) of subjects who completed study treatment phase, discontinued study treatment, primary reason for study treatment phase discontinuation (based on the 'Treatment disposition' page), with % based on FAS subjects.
- Number (%) of subjects who have entered post-treatment follow up phase, completed the follow up phase, discontinued from follow up phase and reasons for discontinuation (based on Follow-up disposition page), with % based on FAS subjects.

Subject disposition data will be listed.

Screened subjects not treated will be listed.

Protocol Deviations

The number (%) of subjects in the FAS with any protocol deviation will be tabulated by deviation category (as specified in the edit checks specifications). All protocol deviations will be listed.

In addition, pandemic related protocol deviations will be summarized by category and relationship. All COVID-19 related protocol deviations will also be listed.

2.3.2 Demographics and other baseline characteristics

Demographic and other baseline characteristics will be listed and summarizes descriptively for all subjects in the FAS.

Continuous variables will be summarized using n, mean, standard deviation (SD), lower quartile (Q1), median, upper quartile (Q3), minimum, and maximum. Categorical variables will be summarized using frequency and percentage.

Following demographic variables will be summarized:

- Age (years)
- Ethnicity
- Race

Following baseline characteristic variables will be summarized:

- Height (cm)
- Weight (kg)
- BMI (kg/m²)
- VOC events

Medical History

Any condition recorded on the Medical History CRF will be coded using the MedDRA dictionary. These will be summarized by system organ class (SOC) and preferred term (PT) of the MedDRA dictionary. The MedDRA version used for reporting will be specified in the CSR and as a footnote in the applicable tables/listings.

Following are the examples of the procedures that will be performed at the baseline:

- Background medical information including sickle cell and VOC history, priapism history, blood transfusion history, leg ulcer, ECG, cardiac imaging and urine protein/creatinine ratio.
- Relevant and current medical history; SCD genotypes (HbSS, HbS β^0 , HbSC, HbS β^+ , and others).
- Concomitant medication use; history of analgesic and hydroxyurea use.
- Complete physical examination.
- Vital signs (blood pressure, pulse measurement, respiratory rate, oxygen saturation, and body temperature), weight and height.
- Clinical laboratory evaluations
- Chest X-ray, if none has been performed within 3 months of Day 1

Drug, alcohol and smoking history will also be collected.

All above baseline characteristics will be summarized and listed.

Analyses will be based on FAS subjects.

2.4 Treatments (study treatment, rescue medication, concomitant therapies, compliance)

2.4.1 Study treatment / compliance

The Safety set will be used for the analyses below. Categorical data will be summarized as frequencies and percentages. For continuous data, n, mean, standard deviation (SD), lower quartile (Q1), median, upper quartile (Q3), minimum, and maximum will be presented.

The duration of exposure in weeks to study drug as well as the dose intensity (computed as the ratio of actual cumulative dose received and actual duration of exposure) and the relative dose intensity (computed as the ratio of dose intensity and planned dose intensity), will be summarized descriptively.

The number (%) of subjects with dose interruption or permanent discontinuation and the reasons will be summarized.

All dosing data will be listed.

Duration of exposure to study treatment

Duration of exposure to study treatment (week) = ((last date of exposure to study treatment) – (date of first administration of study treatment) + 1)/7.

The last date of exposure to study treatment the earliest of the last date of treatment + 27 days, the date of death (if the subject died), and the date of data cutoff.

Summary of duration of exposure of study treatment in appropriate time units will include categorical summaries (less than 1 weeks, at least 4 weeks, at least 14 weeks, at least 26 weeks, at least 52 weeks) and continuous summaries (i.e. mean, standard deviation (SD) etc.).

Cumulative dose

Cumulative dose of the study treatment is defined as the total dose given during the study treatment exposure and will be summarized.

The planned cumulative dose refers to the total planned dose as per the protocol up to the last date of investigational drug administration.

The actual cumulative dose refers to the total actual dose administered, over the duration for which the subject is on the study treatment as documented in the Dose Administration CRF.

Dose intensity and relative dose intensity

Dose Intensity (DI) for subjects with non-zero duration of exposure is defined as follows:

DI (mg/kg/28 days) = Actual Cumulative dose (mg/kg) / Duration of exposure to study treatment (week) × 4.

Planned dose intensity (PDI) is defined as follows:

PDI (mg/kg/28 days) = Planned Cumulative dose (mg/kg) / Duration of exposure (week) × 4.

Relative dose intensity (RDI) is defined as follows:

RDI = DI (mg/kg/28 days) / PDI (mg/kg/28 days).

DI and RDI will be summarized.

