## **6.5 Dose modification**

If a subject does not tolerate the protocol-specified dosing schedule, dose interruptions are either recommended or mandated in order to allow subjects to continue the study treatment until the next scheduled dose. Dose reductions are not allowed.

If a subject experiences drug-induced toxicity, the subject should be closely monitored and a decision to continue or discontinue the subject from the study should be done at the next scheduled dose.

These dose interruptions are summarized in [Table 6-2](#). Deviations to mandatory dose interruptions are not allowed. Permanent treatment discontinuation is mandatory for specific events indicated as such in [Table 6-2](#).

Dose interruptions must be recorded in the Dosage Administration Record CRF. Every effort should be made to maintain the subject on the protocol-defined dosing schedule. In case of dose delay for any reason, the dose should be given as soon as possible. If that infusion visit occurs within  $\pm$  7 days of a protocol-scheduled visit, then the dose and all required assessments will be assigned to the nearest protocol-scheduled visit. However, if that infusion visit does not fall within  $\pm$  7 days of a protocol-scheduled visit, the dose and corresponding assessments will be documented as an unscheduled visit. At that point, every effort should be made to bring the subject's infusions back onto the protocol-defined schedule (within the  $\pm$  7 day window).. If a subject misses two consecutive doses of crizanlizumab due to ADR (i.e., an AE attributable to study drug), the subject should be discontinued from crizanlizumab. A subject with Grade 3 or 4 IRR will be permanently discontinued from crizanlizumab. A subject with a Grade 4 ADR will be permanently discontinued from the study.

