2.1.1 General definitions

Study treatment: Study treatment refers to Crizanlizumab (SEG101) 5.0 mg/kg provided by IV infusion.

Study treatment start and end date: Study treatment start date is defined as the first date when a non-zero dose of study drug is administered and recorded on the Drug Administration Record (DAR) CRF page. Similarly, study drug end date is defined as the last date when a non-zero dose of study drug is administered and recorded on the DAR CRF page of the core study.

Baseline: Baseline period is defined as 12 weeks screening period prior to the first infusion of crizanlizumab 5 mg/kg at Week 1 Day 1.

- For the analysis purpose, in the tables and figures, baseline is considered from Day -91 to one day prior to dosing. Similarly, for "by week 26 analysis" from the first dose date to one day prior to Week 27 Day 1 visit date and for "by week 52 analysis" from the first dose date to one day prior to Week 53 Day 1 visit date will be considered.
- For subjects missing "Week 27 Day 1" visit or "Week 53 Day 1" visit, the scheduled visit day will be considered for cut-off.
- For listings, all available data will be considered.

For safety evaluations, the last available assessment on or before the date of start of study treatment is taken as "baseline" assessment. In case time of assessment and time of treatment start is captured, the last available assessment before the treatment start date/time is used for baseline.

For safety parameters (e.g. ECGs), where study requires multiple replicates per time point, the average of these measurements will be calculated for baseline (if not already available in the database).

In cases where multiple measurements meet the baseline definition, with no further flag or label that can identify the chronological order, then the following rule should be applied: If values are from central and local laboratories, the value from central assessment should be considered as baseline. If multiple values are from the same laboratory (local or central) or collected for ECGs or vital signs, then the last entry should be considered as baseline.

If subjects have no value as defined above, the baseline result will be missing.

Post baseline: Any measurements taken after baseline will be considered as post-baseline measurements.

Change from baseline: Post baseline value – baseline value

Percent change from baseline: (Post baseline value – baseline value) *100/ Baseline value;
(relative change from baseline).

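### Relative dose intensity (RDI) can exceed 100%, or conceal a missed infusion, when the last infusion is early, because SAP 2.4.1 cuts planned dose at that infusion's calendar date; RDI also largely ignores delays

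*SAP*

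**What the plan says.** SAP 2.4.1 defines three linked quantities.

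- Planned cumulative dose: "The planned cumulative dose refers to the total planned dose as per the protocol up to the last date of investigational drug administration". SAP 2.1.1 fixes that date by actual administration: "study drug end date is defined as the last date when a non-zero dose of study drug is administered".
- Actual cumulative dose: "The actual cumulative dose refers to the total actual dose administered, over the duration for which the subject is on the study treatment".
- Intensities: "DI (mg/kg/28 days) = Actual Cumulative dose (mg/kg) / Duration of exposure to study treatment (week) × 4" and "PDI (mg/kg/28 days) = Planned Cumulative dose (mg/kg) / Duration of exposure (week) × 4". RDI is the first divided by the second.

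The only exposure duration the SAP defines is the subject's own. It runs from the first infusion to 27 days after the last, or to death or data cut-off if earlier.

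Protocol Table 6-1 schedules 5 mg/kg at Weeks 1, 3 and 7 and then every four weeks to Week 51. Protocol Section 8 allows a window of 3 days either side at Week 3 and 7 days either side at later dosing visits. For an infusion within 7 days of a scheduled visit, Protocol 6.5 says "then the dose and all required assessments will be assigned to the nearest protocol-scheduled visit". Outside that range the infusion is documented as an unscheduled visit. SAP 2.4.1 does not refer to this rule.

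**The concern.** There are two separate problems.

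**Calendar cut-off.** If the last infusion falls before its nominal day but within the window, its own scheduled date has not yet arrived. The dose enters the numerator and not the denominator. RDI then exceeds 100% although nobody received more infusions than planned, and the surplus can cancel a real omission earlier in the course.

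**Shared duration.** Both intensities are divided by the same actual duration, so planned intensity falls in step with actual intensity when a subject runs late. A reader would expect an intensity ratio to show slippage against the schedule; this one mostly cannot.

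What is at stake is the reading of the exposure table. In a single-arm trial, a weak efficacy result raises the question of whether the drug was delivered as planned. RDI is the summary that sets delivery against plan.

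**Working it through.** The documents state no RDI figure to reproduce, so the SAP formulas were applied to the protocol schedule.

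**Inputs.** Day = (week - 1) × 7 + 1 (SAP Table 2-1). This gives infusions on Days 1, 15, 43, 71, 99, 127, 155, 183, 211, 239, 267, 295, 323 and 351: 14 infusions, or 14 × 5 = 70 mg/kg.

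**Formulas.** With L the day of the last infusion and no death or cut-off before L + 27:
- Duration = (L + 27 - 1 + 1)/7 weeks.
- Planned dose = 5 × number of scheduled days on or before L.
- RDI = (actual/duration)/(planned/duration) = actual/planned.

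**Check on an on-time subject.** Duration = 378/7 = 54 weeks; DI = PDI = 70/54 × 4 = 5.185 mg/kg/28 days; RDI = 100%.

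**Early last infusion.** One day early after k infusions gives k/(k - 1).

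| Case | Actual / planned (mg/kg) | RDI, SAP text |
|---|---|---|
| 14 infusions, last on Day 350 | 70/65 | 107.7% |
| Stops after 8, last on Day 182 | 40/35 | 114.3% |
| Stops after 3, last on Day 42 | 15/10 | 150% |
| Stops after 2, last on Day 14 | 10/5 | 200% |
| Week 31 missed, last on Day 351 | 65/70 | 92.9% |
| Week 31 missed, last on Day 350 | 65/65 | 100% |

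The last two rows show the limit of the concealment: the missed infusion disappears only when the last one is early.

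**Late infusions.** Full course, last on Day 371 (20 days late): duration = 398/7 = 56.86 weeks. DI falls to 70/56.86 × 4 = 4.925, PDI falls to the same value, and RDI is 100%. No dosing day is scheduled after Day 351, so no delay of a full course can show. In a shorter course, a delay shows only once the last infusion reaches the next scheduled dosing day. Eight infusions with the fourth to eighth all 27 days late give 40/40 = 100%; at 28 days late they give 40/45 = 88.9%.

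**How often.** The documents do not say how infusion days spread over the window. Among full-course subjects with no missed infusion and a last infusion in its window, the share showing 107.7% could be anything from 0 to 100%, and mean RDI anything from 100% to 107.7%. If the last infusion is spread evenly over the 15 allowed days (an assumption), 7/15 = 46.7% show 107.7%, and the mean is 100 + 7.7 × 7/15 = 103.6%.

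**Under the repair.**

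| Case | SAP text | Planned dose by visit | By visit, with planned duration |
|---|---|---|---|
| Full course, last 1 day early | 107.7% | 100% | 378/377 = 100.3% |
| Week 31 missed, last 1 day early | 100% | 92.9% | 4.828/5.185 = 93.1% |
| Full course, last 20 days late | 100% | 100% | 378/398 = 95.0% |

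**Why planned duration needs the same truncation.** Take an on-time subject whose eighth infusion, on Day 183, falls on the data cut-off. Actual duration is 183 days. An untruncated planned duration is 183 + 27 = 210 days, giving RDI = 210/183 = 114.8%. Truncating both gives 100%.

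**The case against.** The best defence of the calendar cut-off is that the SAP counts planned dose according to the protocol, and Protocol 6.5 assigns in-window infusions to visits. A programmer who counted that way would get 100% for the subject one day early and 92.9% for the missed Week 31 infusion. Programming specifications are held in a separate document. This has weight, but the SAP sentence names a date and not a visit, so two programmers could produce different tables. Counting by visit also leaves the shared duration in place.

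On the shared duration, the defence is that a ratio of actual to planned cumulative dose is a coherent measure, and that Protocol 12.3 does not say which duration planned intensity should use. DI itself falls with delay and is summarised. That stands: it is a choice the SAP should state, and only the calendar cut-off produces a wrong figure. The PDI formula omits the words tying duration to study treatment, but no other duration is defined.

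A reader might go further in three ways that the documents do not support.

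- *RDI is the trial's measure of compliance.* Protocol 6.6.1 assesses compliance through supervised administration, recorded in source documents and the Drug Accountability Form.
- *Because "Dose reductions are not allowed" (Protocol 6.5), RDI exists only to detect missed or late infusions.* An infusion interrupted for a reaction and not completed also lowers cumulative dose.
- *Missed infusions are lost to the reader.* SAP 2.4.1 summarises interruptions with reasons and lists all dosing data, and SAP 2.3.1 tabulates and lists protocol deviations.

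**Conclusion.** The calendar cut-off is wrong as written, with consequences limited to the descriptive RDI summary. Followed literally, it gives 107.7% for a complete course with the last infusion in its window but early. Early stoppers get larger values, and one missed infusion is hidden when the last is early. RDI also shows no delay in a full course.

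The extreme values need an unusual subject: 200% requires stopping after two infusions with the second given early. With the planned 36 subjects all treated and the rest at 100%, one such subject would move the mean by 100/36 = 2.8 percentage points and set the reported maximum.

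No efficacy test, sample size, estimand or success rule depends on RDI. The figures above 100% and the hidden omission rest on counting planned doses by calendar date, which is the SAP's literal text. The cancellation of duration does not depend on that reading. The 46.7% and 103.6% rest only on the assumed even spread of infusion days.

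**What to change.** Amend SAP 2.4.1 as follows.

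1. Define planned cumulative dose as 5 mg/kg times the number of scheduled infusion visits up to and including the visit to which the last infusion is assigned under Protocol 6.5. For a last infusion outside every window, use the latest scheduled visit on or before it.
2. Choose one of two statements for planned intensity.
   - If RDI is meant to reflect delays, divide planned dose by the planned duration (scheduled day of that visit plus 27 days), truncated at death or data cut-off by the same rule as actual duration. Keep DI on actual duration.
   - Otherwise, state that RDI is the ratio of actual to planned cumulative dose and that delays are to be read from DI.

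Under the first option, values above 100% can remain when infusions really are early. They are small for a full course: 100.3% one day early and 378/371 = 101.9% seven days early. They are larger for short courses: a third and last infusion on Day 36 gives (15/9 × 4)/(15/10 × 4) = 111.1%. Under either option, doses missed after the last infusion stay outside RDI; eight on-time infusions followed by two missed and a stop give 100%.

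The cost is a few sentences and a small programming change, with some subjects' RDI becoming less favourable. Only the calculation changes; the dosing schedule is untouched.
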